With improved techniques of electrosurgery, several randomized trials - the gold standard of clinical research, were performed. A randomized double blind study (15) performed in 369 patients, showed that diathermy incision is superior compared to scalpel incision with reduced incision time, less blood loss and reduced early postoperative pain. The same advantages have been reported using advanced diathermy technology by Lee et al(16). The mechanism of these positive effects of cutting electrosurgery is that the skin is cut with an electrode delivering pure sinusoidal current, which allows tissue cleavage by rapid cell vaporization without damage to surrounding areas; this may explain the absence of tissue charring and the subsequent healing with minimal scarring (17).

Taking together, the recently published advantages of diathermy in the skin incision could be extremely useful in preventing complications and decreasing maternal morbidity associated with CD. However, there are no clinical trials comparing scalpel and diathermy in the population of pregnant patients undergoing CD. To perform such trials will have direct translational value. In situations of emergency cesarean sections, as an example, it will provide important information on which method will be fastest with the least amount of blood loss.

OBJECTIVE

The objective of this study is to compare scalpel vs. diathermy in abdominal wall incision, in pregnant patients undergoing repeat elective cesarean delivery.

HYPOTHESIS

We hypothesize that the abdominal wall incisions made by diathermy compared to scalpel during repeat cesarean delivery will have less incision time, as well as less blood loss. Further we hypothesize that the use of diathermy, compared with scalpel will not increase post-operative pain.

METHODS

- 1) This is a randomized prospective study in women undergoing elective repeat cesarean delivery or repeat unplanned non-emergent cesarean delivery at Medical Center Hospital in Odessa Texas.
- 2) After informed consent is obtained, women undergoing cesarean delivery will be randomized into two groups:

Group One

Will undergo diathermy to incise the entire abdominal wall, which includes skin, subcutaneous tissue, rectus muscle until the peritoneal cavity is visible.

Group Two

Scalpel will be used to achieve the same aims

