1. Postoperative pain

SELECTION OF PATIENTS

Inclusion Criteria -

1. Multiparous pregnant women 18 – 45 years.
2. Gestational ages 37 weeks to 41 weeks,
3. Undergoing repeat elective or repeat unplanned non-emergent cesarean deliveries.

Women with medical comorbidities like hypertension, diabetes complicating pregnancy, pregnant women with or without prenatal care, and multiple gestations will also be included.

Exclusion Criteria –

1. Informed consent can't be obtained in a manner that allows for no impression of undue influence/pressure or sufficient time for patient to consider participation.
2. Primary Cesarean deliveries – as these can bias the selection.
3. Skin conditions such as infections, psoriasis, and eczema.

RECRUITMENT PLAN

Patients from University Women's Health Centre (Texas Tech OBGYN clinic) and also from Medical Center Hospital, Odessa, Texas will be recruited. Potential participants will be identified by a member of the study team or clinic/hospital personnel caring for the patient. In the latter case, study personnel will be contacted to meet the patient after the patient has expressed an interest in learning more about participation. All the participants will have the study procedures, risks, benefits and alternatives explained by a member of the study team.

Once informed consent is obtained they will be randomized with 1:1 allocation by a computer generated randomization process. Since the annual rate of cesarean

Protocol version: 1.0

Page 5 of 11

deliveries in the above-mentioned centers ranges 150 to 175, we expect to enroll a total of 100 patients, and we will allocate 50 patients to each group. Assuming a significance level of 0.05 and a power of 80%, and observing that there is a single measurement and null attrition rate, we will be able to detect at least moderate effect sizes ($d=0.50$) when performing independent means comparisons.

RISKS:

Diathermy –

- A. Possibility of poor wound healing,
- B. There are concerns that large or excessive scars may form,
- C. Unanticipated burns on skin, subcutaneous tissues and other vital organs.

Scalpel –

- A. Injury to the major blood vessels.
- B. Injury to the vital organs.
- C. Excessive bleeding

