From the review of recent literature there are some concerns raised regarding the use of diathermy for skin incisions (10, 11, 12). However, we believe that the use of cutting diathermy, as described in our protocol, does not increase patient risk within the study group. First, there is a concern that diathermy, while making skin incisions, may increase the risk of wound complications, as well as delayed wound healing. However these studies differ from ours in a number of ways: A) Most studies claiming increase in risk examine midline abdominal incisions, and our study employs Pfannenstiel skin incision. B) In some studies it is unclear if pure cut mode was employed. The use of a blend mode will cause more lateral spread of current. This may increase the amount of tissue damage, thus promoting wound complications. Our study will employ diathermy only in pure cut mode in a standard setting as per surgeon's preference. A recent Cochrane review, which includes only randomized trials (the highest form of scientific inquiry), found no significant difference in wound complications between scalpel and diathermy (18).

Second, there has been a case report of a severe burn injury on patients back while utilizing diathermy during cesarean delivery (19). The purported mechanism for this burn was an interaction between diathermy and amniotic fluid (19). However in our study, cutting diathermy will be used only in incision of skin, subcutaneous fat and rectus fascia. This use precludes any interaction between diathermy and amniotic fluid.

ADVERSE EVENTS REPORTING:

Any event deemed as an Adverse Event that is possibly related or unexpected to the study will be assessed at each data gathering point and will be reported to the TTUHSC IRB as described in the IRB policies and procedure manual. Monitoring of adverse events will start on the day of surgery.

BENEFITS – There are no guarantees of any benefit to study participants. However, participants may have potential benefits of using electrosurgery which include reducing the amount of blood loss, dry and rapid separation of tissues. For surgeons, there is a reduced risk of accidental cut injuries.

DATA ANALYSIS :

Distributions of operative time, blood loss and post-operative pain will be tested for normal distribution. Student's T test or the non-parametric equivalent will be used to compare these outcomes between the study and control group. Significance level will be set at 0.05.

DATA MONITORING PLAN:

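### Randomisation is tied only to consent, not to the day of surgery, and no concealment is described, so the zero-attrition assumption is unsupported and the arm may be known before the operator is chosen

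*Combined protocol and SAP*

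**What the plan says.** The Recruitment Plan gives one time anchor for allocation: "Once informed consent is obtained they will be randomized with 1:1 allocation by a computer generated randomization process". Methods item 2 likewise places randomisation after consent. Neither section names a place, an interval to surgery or a person who holds the list.

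Recruitment takes place both in an outpatient clinic and in the hospital: "Texas Tech OBGYN clinic) and also from Medical Center Hospital". Under Selection of Patients, eligibility depends on the delivery itself: a repeat cesarean at 37 to 41 weeks, either elective or unplanned but not an emergency. Methods item 1 places the surgery at one hospital.

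The two primary outcomes, incision time and blood loss, are recorded during the abdominal incision (Methods items 5 to 7).

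The sample size paragraph, also in the Recruitment Plan, sets 50 women per group, assumes "a significance level of 0.05 and a power of 80" percent, and claims to "detect at least moderate effect sizes ($d=0.50$) when performing independent means comparisons". It does so "observing that there is a single measurement and null attrition rate". The single measurement is the only support offered for zero loss.

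The protocol does not describe allocation concealment, when the surgical team learns the arm, or how to handle a woman who is randomised but has no eligible cesarean.

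**The concern.** The stated sequence allows a gap between allocation and incision, and two things can go wrong in it.

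- **Loss.** A woman allocated ahead of surgery may deliver vaginally, deliver elsewhere, become an emergency or withdraw. She then counts among the randomised but has neither primary outcome. A single measurement limits loss after the incision. It does nothing about loss between consent and incision.
- **Selection after allocation.** If the arm is known early, the choice of operator or a late exclusion can depend on it. Incision time and blood loss both depend on who operates, and Methods item 4 leaves the diathermy setting to the surgeon. The surgeon cannot be blinded to the instrument and also calls the end of the timed interval (Methods item 5). Keeping the allocation hidden until the last moment is therefore one of the few protections open to this trial.

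The first problem costs power, and it can also bias the comparison if losses differ by arm. The second biases the comparison directly, by an amount the documents give no means to estimate.

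**Working it through.** **Inputs from the protocol**
- Standardised difference d = 0.50, 50 per group, 1:1, stated power 80%, attrition zero (Recruitment Plan).
- Level: "Significance level will be set at 0.05" (Data Analysis). Sidedness is not stated. The hypothesis is directional, in that diathermy "will have less incision time, as well as less blood loss", so both versions are shown.
- Test: Student's t test or its non-parametric counterpart (Data Analysis). The t test is used here.

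**Assumptions**
- The protocol gives no loss rate. Losses of 5%, 10% and 20% are illustrative.
- Loss is taken as equal in both arms and unrelated to outcome, so d stays at 0.50 and only n falls.

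**Step 1: the plan's own figure.** With n per arm, the noncentrality is d × √(n/2), here 0.50 × √25 = 2.50. By the normal approximation, power is Φ(2.50 − z).
- One-sided 0.05: Φ(2.50 − 1.645) = Φ(0.855) = 0.804. The noncentral t with 98 degrees of freedom gives 0.799. The stated 80% reproduces.
- Two-sided 0.05: Φ(2.50 − 1.960) = Φ(0.540) = 0.705. The noncentral t gives 0.697. The stated 80% does not reproduce; 64 per arm would be needed.

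The difference, 79.9 − 69.7 = 10.2 points, exists with no loss at all. It comes from sidedness, not from the timing of randomisation.

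**Step 2: effect of loss.** Replace n by 50 × (1 − loss). The noncentrality becomes 0.50 × √(47.5/2) = 2.437, 0.50 × √(45/2) = 2.372 and 0.50 × √(40/2) = 2.236. Power from the noncentral t:

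| Assumed loss | n per arm | Power, one-sided | Drop (points) | Power, two-sided | Drop (points) |
|---|---|---|---|---|---|
| 0% | 50 | 79.9% | – | 69.7% | – |
| 5% | 47.5 | 78.1% | 1.8 | 67.4% | 2.3 |
| 10% | 45 | 76.1% | 3.8 | 65.0% | 4.7 |
| 20% | 40 | 71.6% | 8.3 | 59.8% | 9.9 |

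The smallest effect detectable with 80% power rises from d = 0.50 to 0.51, 0.53 or 0.56 one-sided, and from 0.57 to 0.58, 0.60 or 0.63 two-sided.

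**Step 3: the cost of covering loss by enrolment.** Keeping 50 evaluable per arm needs 50/0.95 = 52.6, 50/0.90 = 55.6 or 50/0.80 = 62.5, so 53, 56 or 63 randomised per arm. This would restore the numbers but would do nothing about early knowledge of the arm.

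**The case against.** The strongest reply is that the protocol never says women are randomised in clinic. Consent is a precondition for randomisation, not an instruction to randomise at once, and recruiting in a clinic is not the same as allocating there. Some text points towards late allocation. Methods item 2 speaks of randomising women who are undergoing cesarean delivery. Eligibility requires 37 weeks. Unplanned cases, and women without prenatal care, would probably consent in hospital. On that reading most allocation could happen close to surgery, with little loss.

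This stands in part. A reader might infer that women are randomised in clinic well before surgery, that the team knows the arm in advance, and that null attrition contradicts the rest of the plan. The documents support none of these as fact. They leave timing and disclosure open, and nothing written is contradicted. But they do not require late allocation either, and a site that randomised every woman on the day she signed would be following the protocol.

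A reader might also blame attrition for the whole shortfall from 80% to 69.7%. Step 1 shows that it arises with no loss. Nor do women without an eligible cesarean dilute the treatment effect: they have no outcome, so they leave the analysis and reduce n.

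Finally, the remedy has limits. Late release alone is not concealment; that comes from a sealed or centrally held assignment. The surgeon and the timer will still see the instrument, and lap weights or pain scores can still be missing.

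**Conclusion.** The point holds as a weakness in the allocation procedure. Consent is the only time anchor, clinic recruitment is planned, no concealment is described, and the outcomes depend on a later event that may not occur. The zero-attrition assumption is therefore unsupported, and the arm may be known before the operator is chosen or eligibility is settled.

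The effect on power is modest: about 2 points at 5% loss, 4 to 5 at 10% and 8 to 10 at 20%, depending on sidedness. These figures rest on assumed loss rates, equal in both arms, and on d staying at 0.50. The design has no slack, since one-sided power only just reaches 80% with no loss, so any loss takes it below the stated figure. The possible bias from arm-dependent choice of operator or late exclusion matters more, but its size cannot be calculated from the documents. The change should be made before enrolment starts. The unstated sidedness, worth about 10 points, needs its own correction.

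**What to change.** - Keep consent where it is, in clinic or in hospital.
- Release the allocation on the day of surgery, just before incision, once eligibility has been re-confirmed and the operating surgeon named and recorded.
- Use a concealed computer assignment, or sequentially numbered, sealed, opaque envelopes.
- Count the 100 patients from that point, and report separately the women who consented but were never randomised.
- State how a woman who is randomised but has no primary outcome will be handled in the analysis.

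This removes most loss between consent and incision, so that null attrition becomes close to true for the two primary outcomes. It also prevents the choice of operator or a late exclusion from depending on the arm. It adds no power beyond the design's own figure, which stays at 79.9% one-sided or 69.7% two-sided.

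The cost is a short revision of the Recruitment Plan and Methods item 2, plus the logistics of releasing the allocation at surgery with both instruments available. No extra patients or visits are needed.

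### The stated 80% power for d = 0.50 with 50 per group holds only for a one-sided 0.05 test, which the plan never declares; two-sided, power is about 70%

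*Combined protocol and SAP*

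**What the plan says.** The sample size statement is in the Recruitment Plan of the combined protocol and SAP. Recruitment is set by the caseload of the centres: "we expect to enroll a total of 100 patients, and we will allocate 50 patients to each group". The paragraph then says what that number can detect. It begins "Assuming a significance level of 0.05 and a power of 80"%, takes a single measurement and no attrition, and concludes that "we will be able to detect at least moderate effect sizes ($d=0.50$) when performing independent means comparisons".

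Data Analysis says that a Student's "T test or the non-parametric equivalent will be used to compare these outcomes between the study and control group", and that "Significance level will be set at 0.05". It gives neither the number of sides nor a direction, and no other section does.

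The surrounding text points both ways:

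- Hypothesis is directional for the two primary outcomes: diathermy incisions "will have less incision time, as well as less blood loss". The Results section expects the same direction.
- Objective is neutral: "The objective of this study is to compare scalpel vs. diathermy in abdominal wall incision".
- The Background says of such trials in emergencies that "it will provide important information on which method will be fastest with the least amount of blood loss". The Conclusion likewise expects the results to help decide which of the two methods to prefer.

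**The concern.** Fifty per group is too few for 80% power at d = 0.50 under a two-sided 0.05 t test, so the sentence reads as an overstatement unless a one-sided test was meant. Three things follow.

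- **Risk of a missed effect.** If the analysis is run two-sided, the chance of missing a true d = 0.50 on a primary outcome is about 30%, not the 20% implied. A null result would look better supported than it is.
- **A choice left open.** While the number of sides is undeclared, it can be settled after the data are seen. There is a definite band of results, worked out below, in which that choice alone decides significance.
- **Fit to the question.** A one-sided test favouring diathermy could not show scalpel to be better, although the Background and the Conclusion ask which method is. Nor does an unstated one-sided rule have a clear direction for pain, which the same Data Analysis sentence covers: Hypothesis says diathermy will not raise pain, while Results expects it to lower pain.

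**Working it through.** **Inputs**, all from the Recruitment Plan: n = 50 per group, 1:1 allocation, α = 0.05, target power 0.80, d = 0.50, no attrition. The effect is standardized, so no standard deviation is needed, and no dropout adjustment applies.

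**Set-up.** For a two-sample t test, df = 2 × 50 − 2 = 98, and the noncentrality is d × √(n/2) = 0.50 × √25 = 2.5.

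**One-sided 0.05 (reproduces the plan's figure).**

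- The critical t is 1.661, and the noncentral t gives power 0.799.
- The normal approximation gives Φ(2.5 − 1.645) = Φ(0.855) = 0.804.
- Sample size by the normal approximation: 2 × (1.645 + 0.842)² / 0.50² = 49.5 per group. By the noncentral t it is 50.15.
- Detectable d at 80% power: (1.645 + 0.842) × √(2/50) = 0.497. By the noncentral t it is 0.501.

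**Two-sided 0.05 (does not reproduce it).**

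- The critical t is 1.984, and the noncentral t gives power 0.697.
- The normal approximation gives Φ(2.5 − 1.960) = Φ(0.540) = 0.705.
- Sample size by the normal approximation: 2 × (1.960 + 0.842)² / 0.50² = 62.8, so 63 per group. By the noncentral t it is 63.8, so 64 per group (63 gives power 0.795, 64 gives 0.801).
- Detectable d at 80% power: (1.960 + 0.842) × √(2/50) = 0.560. By the noncentral t it is 0.566.

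| α = 0.05, noncentral t | Power at d = 0.50, n = 50 | d at 80% power, n = 50 | n per group for 80% at d = 0.50 |
|---|---|---|---|
| One-sided | 0.799 | 0.501 | 50.15 |
| Two-sided | 0.697 | 0.566 | 64 |

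A simulation of 200,000 trials agrees: 0.800 one-sided and 0.698 two-sided.

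**Where the choice decides the result.** The smallest observed d that reaches significance is critical t × √(2/50):

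- One-sided: 1.661 × 0.2 = 0.332.
- Two-sided: 1.984 × 0.2 = 0.397.

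An observed difference in favour of diathermy from 0.332 up to 0.397 is therefore significant one-sided and not significant two-sided.

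**If the non-parametric option is used.** On normal data the rank test has an efficiency of 3/π relative to the t test, so 50 per group acts like 50 × 3/π = 47.7. Power at d = 0.50 is then about 0.782 one-sided and 0.676 two-sided. The gap between the two readings remains about 10 points.

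**The case against.** The strongest reply is that nothing was miscalculated. The hypotheses for both primary outcomes name a direction, the Results section repeats it, and the one-sided solution of 50.15 per group matches the planned 50 too closely to be chance. On that view the plan lacks a label, and the 10-point shortfall comes from a two-sided convention that the documents do not state. Comparing two groups is neutral wording that also fits a one-sided test. The sentence about which method is fastest sits in the Background and describes the value of such trials; it sets no analysis rule. Finally, 100 patients follows from caseload, not from the power calculation, and a move from d = 0.50 to d = 0.57 is modest. The documents give no clinically important difference that would make 0.57 inadequate.

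Much of this stands. A one-sided calculation is the likeliest source of the 80%, the shortfall is conditional on a two-sided analysis, and the Background sentence is only supporting evidence. The post hoc choice is a possibility that the plan leaves open; nothing shows that anyone intends it.

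The reply still does not supply the missing rule. A directional hypothesis is not a declared one-sided test. Data Analysis, which governs the comparison, names only a Student's t test at 0.05, and an analyst working from it would ordinarily run it two-sided. The stated power would then be wrong. That the sample was fixed by feasibility does not make the power claimed for it correct.

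**Conclusion.** The concern holds. The stated 80% power for d = 0.50 is right only for a one-sided 0.05 test, and no section declares one. Under a two-sided 0.05 t test, power is 69.7%, about 10 points lower, and the effect detectable at 80% power is d = 0.57.

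The size of the shortfall rests on three assumptions: a two-sided analysis, the t test, and the plan's own premise of no attrition. What does not depend on them is that the text is incomplete on either reading. It matters enough to require correction, because this is the plan's only power statement, it covers both primary outcomes, and the same gap leaves their decision rule open.

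**What to change.** State the number of sides in both the Recruitment Plan and Data Analysis, and make the power sentence match. For a two-sided test, suggested wording is:

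- Recruitment Plan: *With 50 women per group and a two-sided significance level of 0.05, the trial has about 70% power to detect d = 0.50 and 80% power to detect d = 0.57.*
- Data Analysis: *All tests are two-sided at the 0.05 level.*

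If a one-sided 0.05 test was intended, declare it and its direction in both sections before results are seen, and confine the conclusions to that direction. The 80% figure can then stay. The trial could not then conclude that scalpel is better, so the Conclusion should be worded accordingly.

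The cost is two sentences of text and no extra patients; on the two-sided route the stated power becomes less favourable. Keeping 80% power at d = 0.50 with a two-sided test would instead need 64 per group, 128 in total, which is 28 more than planned. The correction does not require that.

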- 3) Only patients undergoing elective repeat cesarean delivery will be enrolled, this will decrease the likelihood of introducing bias into the outcome measures, as well as it will make the population more uniform.
- 4) A standardized abdominal wall incision will be made with either diathermy in cut mode or scalpel. Diathermy will be set in a cut mode with standard setting as per surgeon's preference. All patients in the study will get standard skin incision in terms of length and depth which will be marked by a ruler.
- 5) Incision start and stop time will be recorded by a "timer". A digital wall clock in the OR will be used to establish time. The timer will instruct the surgeon to "cut". The timer will record the time. Once the surgeon reaches the abdominal peritoneum, they will announce "stop". The timers will record the time. The incision time will be the difference between the "cut" and "stop" times. These times will be recorded in units of seconds.

- 6) Along the incision depth the bleeding points will be mopped with sponge laps, no suction will be used and total blood loss will be calculated by weighing the laps.
- 7) Blood loss will be recorded as follows: A "used" lap sponge will weighed. A "fresh" lap sponge will be weighed. These weights will be recorded. Blood loss will be calculated as the differences in these two weights. These weights will be recorded in grams.
- 8) As per standard of care spinal or epidural anesthesia will be administered by certified registered nurse anesthetist (CRNA). Post-operative pain will be managed as follows: 1) 300 micrograms of Morphine sulfate will be injected through then spinal needle or epidural catheter at the beginning of the case. 2) 30 milligrams of Toradol will be injected IM, in the left thigh, at the conclusion of the case. 3) 10 mg hydrocodone/325mg acetaminophen 1-2 tablets, per oral, every 4-6 hours, PRN pain.
- 9) Post-operative pain will be measured by a Numeric Pain Rating Scale (see below) scored as 0= no pain, up to 10= worst possible pain. This score will be assessed daily by resident staff at 6:00 to 7:00 AM from post –op day 1 until hospital discharge.
- 10) As per standard MCH protocol, within one hour preoperatively, Ancef 2-3gms will be administered IV. If the patient is Penicillin allergic, she will receive either 900 milligrams of Clindamycin or 1gram of Vancomycin.

OUTCOMES-

Both groups will be assessed for

Primary outcomes:

1. Incision time
2. Blood loss

Secondary outcome:

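### Adverse events are assessed only if judged related or unexpected, with no blinding stated and no by-arm summary planned, so the trial could not support a comparison of wound harms

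*Combined protocol and SAP*

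**What the plan says.** The adverse-event procedure is two sentences under ADVERSE EVENTS REPORTING. The first sets the rule: "Any event deemed as an Adverse Event that is possibly related or unexpected to the study will be assessed at each data gathering point". Such an event then "will be reported to the TTUHSC IRB as described in the IRB policies and procedure manual". The second gives only a start: "Monitoring of adverse events will start on the day of surgery". No assessor, event list, event definition or end of monitoring is given.

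RISKS gives a separate list for each arm. The diathermy list opens with "Possibility of poor wound healing" and adds scarring and burns. The scalpel list opens with "Injury to the major blood vessels" and adds organ injury and heavy bleeding. The discussion that follows acknowledges published concern about wound complications and slow healing after diathermy, and states the team's belief that its use of cutting diathermy "does not increase patient risk within the study group".

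OUTCOMES names incision time, blood loss and pain. DATA ANALYSIS begins "Distributions of operative time, blood loss and post-operative pain will be tested for normal distribution" and compares those three by t test or a non-parametric equivalent. The last scheduled assessment of each woman is the daily pain score, taken "from post –op day 1 until hospital discharge" (METHODS, item 9). Blinding is not mentioned for any role in this trial. CONCLUSION says the results can help settle which incision method to prefer.

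**The concern.** The rule puts a judgement before the record. An event has to be called an adverse event, and then called either possibly related or unexpected, before the plan says anything is done with it. Both calls can depend on the arm. Relatedness is judged against an incision method that the operating staff know. Expectedness is naturally judged against the RISKS lists, and those differ by arm.

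If capture differs by arm, the counts cannot be read as a comparison in either direction. Even if it does not, no event would be tabulated by arm, because DATA ANALYSIS covers only the three outcomes and gives no method for yes/no events. The trial could then recommend an incision on time, blood loss and pain while having nothing reliable to say on the wound harms that its own RISKS section raises against diathermy. An event that was not recorded at the time may not be recoverable later.

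**Working it through.** **Inputs.** From the protocol: 50 women per arm and no attrition (RECRUITMENT PLAN); the capture rule (ADVERSE EVENTS REPORTING); the two risk lists (RISKS). The plan states no event rate and no figure for adverse events. Its only power statement concerns comparisons of means, so there is no figure to reproduce on this point. All event rates and capture fractions below are assumptions.

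**Step 1: apply the rule to one event.** Take delayed wound healing, and suppose the RISKS lists define what is expected.

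- After diathermy it is listed, so it is expected. It passes only if judged possibly related.
- After scalpel it is not listed. It passes if called unexpected. It fails if the assessor regards it as an ordinary consequence of the cesarean, and so as neither unexpected nor related to the study.

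The same event thus meets a different test in each arm. The text does not show which arm loses more.

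**Step 2: effect on the recorded comparison.** Recorded risk ratio (diathermy/scalpel) = true risk ratio × (capture in diathermy ÷ capture in scalpel). Expected recorded count = 50 × true risk × capture. With a true ratio of 1.0 and an assumed true risk of 10% in both arms (5 events each):

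| Assumed capture, diathermy / scalpel | Expected recorded counts | Recorded ratio |
|---|---|---|
| 90% / 60% | 4.5 / 3.0 | 1.5 |
| 60% / 90% | 3.0 / 4.5 | 0.67 |
| 70% / 70% | 3.5 / 3.5 | 1.0 |

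The ratio does not depend on the assumed 10%. At 5% the first row is 2.25 / 1.5, and at 2% it is 0.9 / 0.6, both with ratio 1.5. The third row matters: losing events equally in both arms lowers the counts but does not bias the ratio.

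**Step 3: what complete capture could show.** With 0 events in 50, the exact two-sided 95% upper limit is 1 − 0.025^(1/50) = 0.0711, or 7.1%. Power to detect a doubled risk with 50 per arm at two-sided 0.05:

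| Assumed risks | Normal approximation | Fisher exact | n per arm for 80% (normal approximation) |
|---|---|---|---|
| 2% vs 4% | 8.4% | 0.6% | 1141 |
| 5% vs 10% | 15.5% | 6.3% | 435 |
| 10% vs 20% | 28.6% | 19.5% | 199 |

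A test of events would be uninformative at this size. Counts with intervals are the honest summary.

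**The case against.** The strongest reply is that this is a 100-woman trial with no safety endpoint, and that the sentence at issue is an IRB reporting rule, not a data-collection rule. The following sentence, on when monitoring starts, carries no relatedness filter. The rule also admits unexpected events whatever their relatedness. Staff outside the study team check the data for accuracy and completeness (DATA MONITORING PLAN). Bleeding at the incision, which is close to one of the listed scalpel risks, is weighed in every woman and compared as a primary outcome.

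Much of this stands, and it rules out several stronger readings that a reader might infer:

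- *That the assessor knows the arm.* The documents do not say who judges. The operating staff must know the instrument; for the residents who make the daily assessments it is plausible but unstated.
- *That counts will be biased, with scalpel wound events the ones lost.* Bias requires unequal capture. An unlisted wound event after scalpel may enter as unexpected, so the direction is open. Infection is on neither list.
- *That the trial plans to conclude that diathermy is safe.* The statement that it adds no risk is a pre-trial belief argued from the literature. HYPOTHESIS and RESULTS speak of time, blood loss and pain. The only no-harm hypothesis concerns pain, which is measured and compared.

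The reply does not supply what is missing. No other event collection is described. Checking recorded data against source is not blinded adjudication. No event count is to be shown by arm.

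**Conclusion.** The point holds in a limited form. Capture rests on an undefined judgement, blinding is not stated for any role, and the arms have different risk lists, so event counts may be biased in an unknown direction. No by-arm summary of events is planned beyond measured blood loss. As written, the trial could not support a comparative statement on wound harms. It is a gap in the safety record and does not affect the planned comparisons of time, blood loss and pain.

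The size cannot be derived from the documents. Under assumed capture of 90% and 60%, a true ratio of 1.0 would be recorded as 1.5 or 0.67; with equal capture it stays at 1.0. The conclusion assumes that the reporting sentence also governs collection, which is the likely reading but not an explicit one, and that the IRB manual, which is not part of the documents, does not supply the missing procedure.

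**What to change.** Before enrolment:

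1. Keep the IRB reporting rule as it stands, and separate recording from attribution. For every woman in both arms, complete one identical yes/no checklist at the end of surgery and at each existing daily visit, whatever the judged relatedness. Give each item a brief definition: wound complication or delayed healing (including infection or breakdown), burn, major vessel injury, vital organ injury, excessive bleeding. Leave scarring out, because it cannot be judged before discharge and a column of zeros would give false reassurance.
2. Add to DATA ANALYSIS a descriptive by-arm table of counts, with exact 95% confidence intervals for each arm and an interval for the difference, and no hypothesis test.
3. Require any safety statement in the final report to cite those intervals and to be limited to the in-hospital period.

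The pre-trial risk rationale under RISKS need not be reworded, since it rests on literature and the trial's intervals do not yet exist.

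The cost is slightly more recording per visit and one table, with no extra patients or visits. The intervals will be wide, which makes any safety statement more guarded. The checklist reduces filtering by relatedness; it does not remove unblinded assessment.
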